#### 5.8 Safety Assessment

The primary safety assessment will be based upon measured methemoglobin levels and hemodynamic indices during the Sodium Nitrite infusion. Because of the exploratory nature of this trial, all potential Adverse Events will be recorded for review.

#### 5.9 Efficacy Assessment

The primary efficacy assessment will be the incidence of PGD Grade 3 or greater in comparison to age and disease-matched historical controls for the UPMC Lung Transplantation program.

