#### Phase of Development: Phase II A

#### **Objectives:**

Primary Objective(s):

 To evaluate the safety of Sodium Nitrite infusion into the procured lungs and lung transplant recipient as reflected in blood mean arterial pressure and methemoglobin levels.

Secondary Objectives:

- To evaluate the efficacy of Sodium Nitrite infusion into the procured lungs and the lung transplant recipient in the prevention of grade 2-3 Primary Graft Dysfunction.
- To evaluate the efficacy of Sodium Nitrite infusion into the procured lungs and the lung transplant recipient in the prevention of delayed allograft complications including the incidence of acute rejection and BOS
- To identify the pharmacokinetic relationship of Sodium Nitrite and

metabolism of sodium nitrite in lung transplant recipients using blood sampling measures before and after drug exposure (will measure levels of plasma and whole blood nitrite, plasma nitrate, red cell iron-nitrosylhemoglobin, S-nitroso-hemoglobin and methemoglobin).

Statement of Primary Efficacy Hypothesis and Primary Analysis:

The administration of Sodium Nitrite at the time of organ procurement and transplantation will be safe and significantly reduce the rate of Primary Graft Dysfunction in patients undergoing lung transplantation.

**Planned Sample Size**: A total of 8 subjects will be enrolled into the protocol. Recruitment is expected to continue for six months.

Study Design: Phase IIA observational non-randomized cohort.

**Diagnosis and Key Patient Selection Criteria:** Males or females greater than 18 years of age or older undergoing lung transplantation.

**Treatments:** Sodium Nitrite infusion to the donor lungs and the lung transplant recipient.

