## 1 Abstract

While increasing numbers of patients with advanced lung disease are candidates for lung transplantation, the short- and long-term outcomes are severely compromised by graft dysfunction, primarily in the form of organ rejection. The earliest manifestation of lung allograft dysfunction, termed primary graft dysfunction (PGD), represents a form of ischemia-reperfusion acute lung injury, and occurs in its severest form (Grade 3) in from 10 to 35% of lung transplant recipients . PGD is the primary cause of early morbidity and mortality after transplantation and is strongly associated with the late development of chronic lung rejection or Bronchiolitis Obliterans Syndrome (BOS) . Early graft dysfunction contributes significantly to the suboptimal outcomes of lung transplantation and to the failure of lung transplant recipients to achieve five-year survival rates comparable to patients who receive other solid organs such as the heart and liver. The risk of PGD further limits the time that lungs can be stored ex-vivo, therefore restricting the pool of available donors. A critical advance in the prevention of both early and late lung allograft dysfunction will occur if PGD can be successfully prevented or minimized.

In this study, we propose to test the hypothesis that administration of Sodium Nitrite to donor lungs and lung transplant recipients at the time of transplantation will be safe and will reduce the incidence of grades 2 and 3 PGD, thereby improving clinical outcomes with minimal toxicity.

Sodium Nitrite will be obtained from a commercial preparation (Hope Pharmaceuticals, Sodium Nitrite Injection USP (30mg/mL) NDC Number 60267-079-02) and the UPMC Pharmacy will prepare the formulations, which will be infused at three time points. First it will be infused into the preservation solution bag at the time of organ procurement from the donor, then to the allograft at the time of transplantation, and finally as a direct infusion into the organ recipient.

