#### 2.2 Hypothesis

Administration of Sodium Nitrite to donor lungs and lung transplant recipients at the time of transplantation will be safe and will reduce the incidence of grades 2 and 3 PGD, thereby improving clinical outcomes with minimal toxicity.

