#### Secondary Objectives:

- To evaluate the efficacy of Sodium Nitrite infusion into the procured lungs and the lung transplant recipient in the prevention of grade 2-3 primary graft dysfunction.
- To evaluate the efficacy of Sodium Nitrite infusion into the procured lungs and the lung transplant recipient in the prevention of delayed allograft complications including the incidence of acute rejection and BOS.
- To identify the pharmacokinetic relationship of Sodium Nitrite and metabolism of sodium nitrite in lung transplant recipients using blood sampling measures **before and after** drug exposure (levels of plasma and whole blood nitrite, plasma nitrate, red cell ironnitrosyl-hemoglobin, S-nitroso-hemoglobin and methemoglobin will be measured).

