#### 2.4 Endpoints

#### Primary Endpoints Analysis

- The primary endpoint for the safety of Sodium Nitrite administration will be assessed by measurement of methemoglobin levels and mean arterial pressure during the nitrite infusion in the transplant recipient.
- The primary endpoint for the efficacy of Sodium Nitrite infusion will be the incidence of grades 2 and 3 PGD using the International Society for Heart and lung transplant (ISHLT) criteria for PGD based upon the worst value obtained over the initial 72 hours post lung reperfusion (T0-72).

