#### 5.7.2 Study monitoring

#### 1) Required end points during study drug infusion

• Mean Arterial Pressure:

The recipient's mean arterial pressure (MAP) will be monitored at 1 minute intervals during study drug infusion followed by 15 minute intervals for 1 hour.

• Nitrite and metabolite levels:

Blood samples will be obtained prior to the infusion; at 5, 30, and 60 minutes during the infusion; and at 5, 10, 30, 60, 90, 150 after the infusion to measure plasma and whole blood nitrite, plasma nitrate, red cell iron-nitrosyl-hemoglobin, S-nitroso-hemoglobin and methemoglobin concentrations. However, no sample will be sent for methemoglobin concentration prior to drug infusion. Blood samples will also be obtained every 24 hours for two days for future exploratory biomarker/proteomic studies which would include evaluation of IL6, IL $\beta$ , TNF-a, iNOS and COX-2. Nitrite levels will be measured by established methodologies (ozone-based reductive chemiluminescence) routinely performed in [name] NO Metabolomics Core facility.

2) Required end points post study drug infusion to hospital discharge

Following administration of the Sodium Nitrite, the study subjects will continue to receive usual care for their condition consistent with local transplant treatment protocols. The study will not introduce any modification to the normal care algorithms. Day 0 ( $D_0$ ) will be defined as the day of transplantation and reperfusion. Subsequent study days will be numbered sequentially. The following parameters will be required for collection prospectively. They will be obtained specifically for the study protocol if not requested by the treating physician. If requested by the treating physician the parameters will be recorded from the medical record. Specific parameters required to be monitored following lung transplantation/reperfusion will include:

• Arterial blood gas measurements from D0 to D3

The  $Pa0_2/FiO_2$  ratio and oxygenation index will be calculated based upon an arterial blood gas at D0 (within 6 hours of reperfusion), and D1, D2, and D3. The initial measurement (D0) will be obtained on a FiO2 of 1.0 and PEEP of 5 while on mechanical ventilation. Subsequent measurements will be obtained on the prescribed ventilator settings. Ventilator parameters will be obtained with each blood gas determination. **There will be no arterial blood gas measurement on days patient is extubated.** 

• Chest radiography from D0 to D3

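### Section 5.9 bases the primary efficacy assessment on grade 3 PGD alone, while Section 2.4, the objectives and the hypothesis use grades 2 and 3

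*Combined protocol and SAP*

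**What the plan says.** Section 2.4 (Primary Endpoints Analysis) says that the primary efficacy endpoint "will be the incidence of grades 2 and 3 PGD using the International Society for Heart and lung transplant (ISHLT) criteria for PGD", based on the "worst value obtained over the initial 72 hours post lung reperfusion". Four other places use the same two grades:

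- the synopsis objective, "in the prevention of grade 2-3 Primary Graft Dysfunction";
- the abstract, "will reduce the incidence of grades 2 and 3 PGD, thereby improving clinical outcomes";
- the hypothesis in Section 2.2, "will reduce the incidence of grades 2 and 3 PGD";
- the secondary objectives in Section 2.3, "in the prevention of grade 2-3 primary graft dysfunction".

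Section 5.9, the only place that names a comparator for PGD incidence, reads: "The primary efficacy assessment will be the incidence of PGD Grade 3 or greater in comparison to age and disease-matched historical controls". It gives no time window and does not refer back to Section 2.4.

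The grading table in Section 5.7.2 runs from 0 to 3. Patients who need extracorporeal support or inhaled nitric oxide are assigned grade III, so nothing lies above that grade.

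Section 6 calls the analysis exploratory and disclaims firm conclusions. It describes comparison with historical controls through least-square means for continuous variables and does not restate the PGD definition.

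**The concern.** Both Section 2.4 and Section 5.9 use the word primary for efficacy, and no rule says which governs. On a scale that ends at 3, the words or greater add nothing, so Section 5.9 read literally leaves out every grade 2 case. An analyst who follows it reports a different quantity from the one in the hypothesis.

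What is at stake is how eight patients are read against a historical rate. The two cuts have different background rates, so the same result looks more or less striking depending on the cut. With both written down as primary, the cut could be chosen once the grades are known. That matters even in a pilot, because the abstract and Section 4 say positive results are expected to lead to a larger trial.

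**Working it through.** **No figure to reproduce.** The plan states 8 patients, with no power, alpha, target effect or control rate for PGD. The check compares the two definitions and illustrates the gap between them.

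**Step 1: the definitions side by side.**

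| Item | Section 2.4 | Section 5.9 |
|---|---|---|
| Grades counted | 2 and 3 | 3 only (top of the scale) |
| Window | worst value, 0 to 72 h | not given |
| Comparator | not given | age- and disease-matched historical controls |

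The window for study patients is not in doubt. Section 2.4 gives it, and Section 5.7.2 schedules "Arterial blood gas measurements from D0 to D3" and chest films on the same days.

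**Step 2: illustrative benchmark.** Assumption: the local Table 1 row in Section 3 (N=76, T0-72, unpublished, 2003-2004) stands in for the controls, whose rates are not given. It is the only row with the trial's window. Grade 2 is 20% and grade 3 is 25%.

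- Grades 2-3: 20% + 25% = 45%; expected events 8 × 0.45 = 3.6.
- Grade 3 only: 25%; expected events 8 × 0.25 = 2.0.
- Share of grade 2-3 events that are grade 2: 20/45 = 44%.

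**Step 3: how a good result would read.** Binomial, n = 8, no treatment effect.

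- 0 events, grades 2-3: (1 − 0.45)^8 = 0.0084, or 0.8%.
- 0 events, grade 3: (1 − 0.25)^8 = 0.1001, or 10.0%.
- At most 1 event: 0.063 for grades 2-3, 0.367 for grade 3.

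**Step 4: would the two counts differ?** They differ if at least one patient has grade 2 as the worst grade. At 20% the chance is 1 − 0.80^8 = 83%. At 8%, the lowest grade 2 figure in Table 1 (a single time point, T48), it is 1 − 0.92^8 = 49%. Both are illustrative.

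**Step 5: range over the Table 1 rows that report both grades.**

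| Row | Grades 2-3 | Grade 3 | Grade 2 share | P(0/8), grades 2-3 | P(0/8), grade 3 |
|---|---|---|---|---|---|
| Local, N=76, T0-72 | 45% | 25% | 20/45 = 44% | 0.55^8 = 0.8% | 0.75^8 = 10.0% |
| N=402, T0-48 | 62% | 34% | 28/62 = 45% | 0.38^8 = 0.04% | 0.66^8 = 3.6% |
| N=334, T0 | 42% | 21% | 21/42 = 50% | 0.58^8 = 1.3% | 0.79^8 = 15.2% |
| Same 334, T48 | 17% | 9% | 8/17 = 47% | 0.83^8 = 22.5% | 0.91^8 = 47.0% |

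The grade 2 share is stable at 44% to 50%. The background probabilities are not. At the low T48 rates, 0/8 would be unremarkable under either cut.

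**The case against.** The strongest reply is that the conflict resolves itself. Five places say grades 2-3, and the words or greater make sense only if a lower grade was meant, so Section 5.9 is a slip that any careful analyst would read through. All grades are collected, so nothing is lost. Efficacy is a secondary objective, there are eight patients, and Section 6 rules out firm conclusions. Most of this stands, and it sets the weight of the point. It does not remove the point, because the text still carries two primary definitions and does not say which governs.

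The benchmark is also weak. The local row is old and unpublished, and the table's caption says the rows use a component of the ISHLT criteria. Sections 7.1.2 and 7.1.4 exclude donors over 55 and recipients with pulmonary hypertension. The background section names donor age and recipient pulmonary hypertension as possible risk factors, so trial rates may be lower. This stands, and the figures are illustrations only.

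A reader might also infer that the historical controls will be graded on a different cut or window from the study patients, which at the local rates would create a 20-point gap (45% − 25%) without any treatment effect. The documents do not support that. They are silent on how controls are graded, no section plans a mismatch, and the ordinary reading of Section 5.9 applies one endpoint to both groups. This is missing detail, not a contradiction.

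**Conclusion.** The conflict between Section 5.9 and Section 2.4 is real and should be corrected. As written, Section 5.9 drops grade 2 cases and departs from the hypothesis. Under the local Table 1 rates, that is 44% of the events Section 2.4 counts: the expected number in eight falls from 3.6 to 2.0, and the background probability of 0/8 rises from 0.8% to 10.0%. These figures rest on the assumption that the local row represents the controls.

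The consequence is confined to interpretation and to the freedom to pick a definition afterwards. A reader might infer that grade 3 was deliberately substituted as the endpoint, or that the efficacy result is invalid. The documents support neither: every other statement of the aim uses grades 2-3, and no confirmatory test depends on the choice.

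**What to change.** Change Section 5.9 to read: *incidence of PGD grade 2 or 3, worst grade over T0-72, as defined in Section 2.4*, against the same matched historical controls, and delete the words or greater. Report grade 3 alone as a supportive result.

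As a clarification only, add one sentence saying that the historical controls are graded with the same cut, window and scoring rules as far as their records allow. List any rule that cannot be applied to them, for example the D0 blood gas on FiO2 1.0 and PEEP 5, the core radiograph review, or the committee's exclusion of other causes.

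The cost of the correction is protocol wording. The clarification may require review of the controls' blood gases and radiographs over 72 hours. Neither needs new patients or new study measurements.

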PGD grade 3 has been associated with a 90-day mortality of 16.2% in comparison to a mortality of 9.5% for subjects with PGD Grades 0-1. However, the prognostic significance of PGD extends well beyond the immediate post-operative period. Grade 3 PGD has been associated with a more rapid decline in post-operative pulmonary function and the late development of bronchiolitis obliterans syndrome (BOS). These data suggest that new approaches to reduce PGD are fundamental to improving the morbidity and mortality in lung transplant recipients.

4.3.1 Complex Interaction of Donor and Recipient Risk Factors Contributing to Primary Graft Dysfunction

Using the standardized definition for PGD, numerous donor, recipient, and treatment variables have been identified as potential clinical risk factors for the development of PGD . These reported associations remain limited by the lack of multicenter, prospective, observational studies using consistent procurement techniques. Despite this limitation, both single center and registry reviews have suggested that variables such as donor age , prolonged ischemia time , recipient pulmonary hypertension , recipient diagnosis , and donor requirement for blood transfusion , may all be independent risk factors for PGD.

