Plain film portable chest radiography will be obtained on D0 (within 6 hours of reperfusion), and D1, D2, and D3. All chest radiography will be referred to a radiology core for independent review and classification independent of the review required for clinical documentation.

Grade	PaO2/FiO2	Radiograph	
0	>300	Absent	
1	>300	Present	
2	200-300	Present	
3	<200	Present	

The primary end point of PGD will be scored using the following criteria:

The absence of pulmonary infiltrates on plain film radiograph will be assigned Grade 0 independent of the PaO2/FiO2 ratio. All extubated patients will be graded as 0 or 1 based upon the interpretation of the chest radiograph. The need for extracorporeal support and/or inhaled nitric oxide will be documented and automatically assigned a Grade III classification.

The diagnosis of Primary Graft Dysfunction (PGD) requires the exclusion of alternative conditions, which might produce a similar radiographic and physiologic pattern including hyperacute rejection, cardiogenic pulmonary edema, venous anastomotic obstruction, and allograft infection. Exclusion of these conditions will be made by a PGD grading committee composed of transplant physicians not involved in the patient's care at the time of transplant until hospital discharge. Medical records will be reviewed within six to eight weeks of transplantation by the committee to classify PGD.

• Sequential Organ Failure Assessment Score (SOFA):

The SOFA score is a recognized ICU scoring system to define the extent of the patient's organ failure. The scoring system has an individual component score for each of 6 organ systems including **respiratory**, **cardiovascular**, **hepatic**, **coagulation**, **renal** and **neurological** systems . The SOFA Score will be obtained daily at D1, D2, D3, and D4.

- Ventilator Free Days (VFD): Defined as the number of days off mechanical ventilationat 8am through D30 post transplantation.
- ICU Free Days (IFD): Defined as the number of days outside the ICU through D30 post transplantation.
- Hospital Days: Defined as the total number of acute and long term acute (LTAC) hospital days during the index transplant admission.

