## 6 Statistical Consideration

Statistical analysis for the protocol will be primarily exploratory (i.e., hypothesis generating), and no firm conclusion will be drawn based upon a confirmation oriented statistical analysis. The results will be displayed as mean±standard deviation for continuous variables, or frequency (percentage), for discrete variables. For variables with skewed distributions, both nonparametric analysis, and parametric analysis using logarithmically transformed data will be performed. The continuous efficacy variables will be analyzed by analysis of variance (ANOVA) models, which will contain terms of treatment dose, disease type, and treatment-by-disease type interaction. The treatment-by-disease type interaction will be assessed at significance level 0.10. If the treatment-by-disease type interaction is not statistically significant, the interaction effect will be removed from the model. The treatment differences will be assessed by pair-wise comparison between the study population and historical controls, using least-square means from the ANOVA model. If baseline value of each continuous efficacy variable is to be adjusted, data will be analyzed by analysis of covariance (ANCOVA).

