#### 7.1.4 Recipient exclusion criteria

- Recipient age > 70 years.
- Recipient history of pulmonary hypertension (idiopathic PAH, or secondary PAH with mean PA > 30 mm Hg)
- Recipient history of abnormal cardiac function defined as prior CABG or LVEF < 45 %)
- Recipient history of open thoracotomy/prior pleurodesis as exclusion criteria. However
  patients who have had limited VATS procedures for biopsies would NOT be excluded
  from the study.Recipient history of cirrhosis
- Recipient history of mechanical ventilation or extracorporeal support pre-operatively

- Recipient pre-operative hypotension defined by a systolic blood pressure less than 90 mm Hg not responsive to intravenous fluids or requirement for vasoactive medications
- Recipient preoperative history of renal insufficiency, dialysis or estimated glomerular filtration rate <30 ml/min/1.73 m^2 BSA
- Patients undergoing retransplantation
- Recipient history of significant coronary artery disease that is flow limiting and unable to be corrected by further percutaneous coronary artery interventions.

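### Historical controls are matched on age and disease only and need not meet the trial's donor and recipient criteria, a selection difference that could favour the drug on PGD

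*Combined protocol and SAP*

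**What the plan says.** Section 5.9 contains the only definition of the control group: the primary efficacy assessment is PGD incidence "in comparison to age and disease-matched historical controls for the UPMC Lung Transplantation program". It does not say whether age means donor or recipient age, and it gives no calendar window.

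The trial population is narrower. Section 7.1.2 excludes, among others, donors over 55, donors with PaO2/FiO2 below 300 and donors ventilated for more than 5 days. Section 7.1.4 excludes "Recipient history of pulmonary hypertension (idiopathic PAH, or secondary PAH with mean PA > 30 mm Hg", along with pre-operative ventilation or extracorporeal support and retransplantation.

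The risk-factor discussion in section 3 (subsection numbered 4.3.1) includes donor age and recipient pulmonary hypertension among variables that "may all be independent risk factors for PGD". It also cautions: "These reported associations remain limited by the lack of multicenter, prospective, observational studies".

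On analysis, section 6 states: "The continuous efficacy variables will be analyzed by analysis of variance (ANOVA) models". The terms are treatment dose, disease type and their interaction. No model is given for a binary outcome such as PGD incidence. Section 6 adds that "no firm conclusion will be drawn based upon a confirmation oriented statistical analysis".

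**The concern.** The treated patients pass through a filter that the controls do not. Part of that filter acts on factors the protocol itself regards as possible causes of PGD. Matching on disease may remove idiopathic pulmonary hypertension, and matching on recipient age may remove recipients over 70. Neither touches the donor criteria, secondary pulmonary hypertension, pre-operative support or retransplantation. The protocol does not give the direction for donor age; I assume that older donors carry more risk. On that reading the controls would be expected to have more PGD than comparable untreated patients, and the drug would look better than it is.

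No planned analysis corrects this, because the section 6 models cover continuous variables only and include no donor factor. There is no concurrent control group either. A larger control pool chosen by the same rule would estimate the wrong benchmark more precisely.

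What is at stake is limited. Safety is the primary objective, and section 6 disclaims firm conclusions. But section 1 expects positive results to lead to a larger trial, and a low PGD count would be read in that light.

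**Working it through.** The plan gives no power, effect size or significance level for the PGD comparison, so there is no figure of its own to reproduce. The check has two parts.

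**1. Does any text apply the trial criteria to controls?** Sections 5.9, 6 and 7 were read together. Section 5.9 names two matching variables. Section 6 mentions historical controls only as the comparator in the least-squares-mean comparisons. Section 7 describes enrolled subjects and their donors. None restricts the controls.

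**2. How large could the effect be?** This is illustration only.

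Inputs:
- Control Grade 3 rate, *b*: 25% as the base case. This equals the Grade 3 figure in the unpublished Pittsburgh row of Table 1 (76 recipients, 2003-2004, worst value over 0-72 hours), but the plan does not say that this cohort will be the control group. Sections 1 and 3 give a 10-35% range for Grade 3.
- *f*: share of controls, after matching, who would fail 7.1.2 to 7.1.4. Assumed 25%, 40%, 50%.
- *RR*: their PGD risk relative to eligible patients. Assumed 1.3, 1.7, 2.0.
- *n* = 8 treated patients.

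The control rate is a mixture of eligible and ineligible patients, *b* = *p*(1 − *f*) + *p*·*RR*·*f*, so the rate in eligible patients is *p* = *b* / (1 − *f* + *f*·*RR*).

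| *f*, *RR* | Divisor | *p* when *b* = 25% | Gap (points) | P(at most 1 of 8), inert drug |
|---|---|---|---|---|
| no selection | 1 | 25.0% | 0 | 0.367 |
| 0.25, 1.3 | 0.75 + 0.325 = 1.075 | 23.3% | 1.7 | 0.412 |
| 0.40, 1.7 | 0.60 + 0.68 = 1.28 | 19.5% | 5.5 | 0.517 |
| 0.50, 2.0 | 0.50 + 1.00 = 1.5 | 16.7% | 8.3 | 0.605 |

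The last column is (1 − *p*)^8 + 8*p*(1 − *p*)^7.

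With the same divisors, *b* = 10% gives *p* = 9.3%, 7.8% and 6.7% (gaps 0.7 to 3.3 points), and *b* = 35% gives 32.6%, 27.3% and 23.3% (gaps 2.4 to 11.7 points).

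Section 2.4 defines the efficacy endpoint as grades 2 and 3, whereas 5.9 uses Grade 3. For grades 2-3 the Pittsburgh row gives 20% + 25% = 45%. The same divisors give 41.9%, 35.2% and 30.0% (gaps 3.1 to 15.0 points), and P(at most 1 of 8) rises from 0.063 to between 0.088 and 0.255.

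**Counterweight.** For the D0-D3 measurements, section 5.7.2 says: "They will be obtained specifically for the study protocol if not requested by the treating physician". If controls were measured less often, more PGD would be found in trial patients, which works against the drug. If control records capture a fraction *d* of the PGD that the trial schedule would find, the observed control rate is *d*·*b*. It equals *p* when *d* = 1 / (1 − *f* + *f*·*RR*), that is 0.930, 0.781 and 0.667 for the three cases. Below that fraction the comparison leans against the drug. These values are reciprocals of the divisors above, so they restate the same assumptions and are not separate evidence.

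A third difference may work the other way. Of diagnoses that mimic PGD, section 5.7.2 says: "Exclusion of these conditions will be made by a PGD grading committee composed of transplant physicians". If the same is not done for controls, this could lower the trial's PGD rate relative to theirs.

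**Precision.** One case in 8 has an exact (Clopper-Pearson) 95% interval of 0.3% to 52.7%.

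**The case against.** The strongest reply is that little rests on this comparison. Safety is the primary objective, the analysis is declared exploratory, and no PGD threshold or go/no-go rule is stated. With 8 patients, an inert drug and perfectly comparable controls, at most 1 Grade 3 case occurs with probability 0.37 anyway, so chance outweighs the illustrated selection effect. The net direction is unproven, *f* and *RR* come from no document, and the risk-factor evidence is acknowledged to be limited. Matched age most naturally means recipient age. An eligibility restriction would still leave ischemia time and donor transfusion, also named in section 3, unaddressed, and grading unequal.

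Most of this stands, and it limits the consequence and the claim about size. It does not remove the defect. Sections 2.4 and 5.9 both give PGD primary status for efficacy, and the historical group is its only comparator. Chance error is at least visible in a confidence interval; a selection difference is not, and the exploratory label does not remove it. An uncertain net direction is itself a reason to define the controls better, since a result in either direction would be hard to interpret.

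The conflict between 5.9 and 2.4 over which grades count is a separate matter that must be reconciled; this point holds under either definition.

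**Conclusion.** The concern holds. Followed as written, section 5.9 produces a benchmark that is not comparable with the trial population on factors the protocol regards as possible PGD risks, and nothing in section 6 adjusts for it. This selection difference could favour the drug. That direction rests on the assumption that the excluded donors and recipients carry higher PGD risk. The net direction, once measurement and adjudication differences are included, is not established.

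The size cannot be obtained from the documents. Under the stated assumptions it is 1.7 to 8.3 percentage points at a 25% Grade 3 control rate. This should be fixed before controls are chosen. It bears on how the PGD signal is read for a later trial, not on the safety objective. Confidence is medium.

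**What to change.** In section 5.9:

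- Restrict controls to UPMC recipients who meet 7.1.2 to 7.1.4 as far as transplant records show, in addition to age and disease matching.
- State whether age is donor or recipient age.
- Fix the calendar window before control outcomes are examined.
- Apply the section 5.7.2 grade definitions to the recorded blood gases and film reports where available.
- Report the PGD comparison with and without the eligibility restriction, with the number of controls that have gases and films on each of D0 to D3.
- State the remaining differences as a limitation: study-driven measurements, core radiology reading and committee review.

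The cost is chart abstraction from existing records, a smaller control pool, and missing criteria or gases for some older cases. The restriction reduces the selection difference but does not make grading equal. Nothing changes for trial patients.
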